8.4.2 Serious Adverse Event Reporting

All SAEs occurring after the first dose and before the last follow-up are collected and recorded. The investigators should carefully fill in the SAE Report Form item by item, and sign and date the report once SAEs occur. The investigators should report the occurrence of SAEs to the sponsor within 24 h after being informed (the requirements on the need to submit the report to the clinical trial institution or the ethics committee vary across the study sites). If a SAE occurs after the last follow-up (within one month after the follow-up) and it cannot be determined as unrelated to the investigational drug, then the follow-up should be continued and recorded for this case until symptom disappearance or recovery to the baseline (or even better than the baseline), or disease stability, or the recovery of any laboratory abnormalities to normal or the baseline level, or loss to follow-up.

8.4.3 Unanticipated Problem Reporting

After receiving safety-related information from any sources, the sponsor should carry out analysis and assessment immediately, including the severity, relevance to the investigational drug, and whether the safety event is expected. The sponsor should immediately report the SUSARs to all participating investigators, clinical trial institution, and ethics committee. In the meantime, the sponsor should report the suspected and unexpected SAEs to the drug administration authorities and the health authorities within the stipulated time. Upon receiving the safety-related information concerning the clinical trial from the sponsor, the investigators should immediately sign and read it and consider whether there is a need to adjust the treatments for subjects. The investigators should communicate with the subjects early if necessary. The SUSARs provided by the sponsor should be reported to the ethics committee as per the requirements developed by the ethics committee within the stipulated time. The day that the sponsor is informed first is denoted as day 0.

The sponsor (or the entrusted CRO) has already built a safety database that conforms to the E2B (R3) standard and implemented management of the safety data. Moreover, relevant terms are coded according to MedDRA (version 23.1 or above).

8.4.4 Events of Special Interest

Not applicable.

8.4.5 Reporting of Pregnancy

The subjects should be told to take strict contraceptive measures during the study before enrollment (including subjects themselves and their partners). If the subjects or their partners get pregnant during the study, the investigators should fill it in the Pregnancy Event Table within 24 h after the confirmation and then submit it to the sponsor. All reporting procedures should conform to the ethical requirements at the study site involved. A pregnancy event is neither an AE nor a

SAE but should be recorded in the CRF as a SAE.

The pregnant subjects should immediately withdraw from the study and the situation should be timely recorded, reported and followed up. If the partners of male subjects get pregnant, the male subjects are not required to withdraw. However, the pregnant partners of the male subjects should be recorded, reported, and followed up in the same way as with the pregnant female subjects. The investigators should communicate with the subjects in a scientific and rigorous way about medication. The subjects should be informed of the potential impact and risks of the investigational drug on the pregnant women and fetuses. Whether to terminate or continue the pregnancy is left to the discretion of the subjects and their partners.

If the subjects and their partners decide to continue the pregnancy, they are required to receive follow-up for pregnancy once every three months until one month after the end of pregnancy. Any abnormalities occurred during the pregnancy should be recorded and reported as SAEs. Except for normal delivery and normal newborns, all other pregnancy outcomes are recorded and reported as SAEs.

Any abnormalities of the newborns should be collected and recorded, and those meeting the criteria for SAEs should be handled according to the procedures for SAEs.

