- 12) History of other severe diseases: ① cardiovascular disease, such as acute myocardial infarction/myocardial infarction within 1 year, acute myocarditis, acute pancarditis, acute heart failure, chronic heart failure NYHA heart function class \geq II (see [Appendix 2](#) for details), CCS class II or higher stable angina pectoris (see [Appendix 3](#) for details), unstable angina pectoris, rheumatic heart disease, malignant arrhythmia [ventricular tachycardia/ventricular fibrillation, frequent ventricular premature beats (more than 5 beats in one minute), II/III degree atrioventricular block, rapid atrial fibrillation/atrial flutter (ventricular rate > 110 beats/min)]. ② brain disease, such as cerebral hemorrhage/cerebral infarction (excluding lacunar infarction), history of epilepsy, pituitary/hypothalamic lesions. ③ lung disease (except lung cancer patients), such as asthma, acute obstructive pulmonary infection, acute bronchitis or acute tracheobronchitis. ④ liver disease (except liver cancer patients), such as cirrhosis (child-pugh score more than 7 points) (see [Appendix 4](#) for details), etc.
- 13) Participants in any other clinical trial within 3 months before screening (excluding participants who only participated in the screening of this clinical trial and have not used the investigational drug).
- 14) Drug/alcohol abuse, severe mental disorders.
- 15) Patients have received high-dose radiation therapy or annual radiation dose >50 mSv within 1 year (inquire about their previous radiation therapy and radiation examination within 1 year, and record them in the screening medical record).
- 16) Patients with claustrophobia, emotional lability, acute persistent spasms, or inability to keep their arms supine for 15 to 30 minutes.

- 17) Female subjects who are pregnant or lactating, or female subjects who have had unprotected sex within 2 weeks before screening, or with positive blood pregnancy test; male subjects (or their partners) or female subjects who have fertility plan or sperm or egg donors throughout the trial and within 6 months after the end of the study, and are unwilling to take contraceptive measures during the trial and within 6 months after the end of the study.
- 18) Women of childbearing age do not use sufficient non hormonal contraceptive methods.
- 19) Any condition that the investigator or primary physician believes may not be appropriate for participating the study.

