6.1.5 Dosing and Administration

Dose of investigational drug: This trial will include 3–4 dose groups, namely the 0.1 mg, 0.3 mg, 0.5 mg and 0.9 mg dose groups. The dose of protein should be adjusted according to the imaging results of the previous dose group during the trial. The radiation dose for all dose groups at the time of administration should be ranged from 37 to 200MBq.

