6.1.10 Tracking of Dose

SNA002 will only be intravenously injected once in the trial.

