7.3 Study Schedule

7.3.1 Screening

D - 14 to D - 2

- Sign the ICF.
- PD-L1 immunohistochemistry results.
- Collect demographic data.

- 4) Inquire and record medical history (including personal history, past history, allergy history, and cancer history).
- 5) Tumor stage.
- 6) Pathological test results within 1 year before screening.
- 7) Vital signs.
- 8) Physical examination.
- 9) 12-lead ECG.
- 10) Cardiac function score: scored according to NYHA standards
- 11) ECOG score.
- 12) Chest x-ray (not required if chest CT results are available).
- 13) Enhanced CT/enhanced MRI/PET-CT (results of examinations conducted at the study site or other tertiary hospitals within 30 days prior to enrollment are acceptable).
- 14) Laboratory tests: blood routine, blood biochemistry, electrolyte, coagulation function, urine routine, serum virology, thyroid function tests, and serum pregnancy test (only for female subjects of childbearing age). Serum virology can accept results within 28 days before screening, while other laboratory tests can accept results within 7 days before screening.
- 15) Review compliance with inclusion/exclusion criteria.
- 16) Record concomitant medications.

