7.3.2 Baseline Period

D-1

- 1) Review compliance with inclusion/exclusion criteria for the second time
- 2) Enrollment (Subjects can be enrolled in the relevant department due to primary tumor before D-1 and after D1 and complete the trial period during hospitalization) .
- 3) Record concomitant medications.

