7.3.7 Schedule of Events Table

Table 4 Schedule of Events Table

Study Period/Visits	Screening Period	Baseline Period	Study Period (5 days)		Safety Follow-up Period (D6-28)		Premature Withdrawal ¹⁸
Study Day (s)	D-14~2	D-1	D1	D2~D5	D6±1d	D28±2d	
Informed consent	x						
Inclusion/exclusion criteria	x	x					

Study Period/Visits	Screening Period	Baseline Period	Study Period (5 days)		Safety Follow-up Period (D6-28)		Premature Withdrawal ¹⁸
Study Day (s)	D-14~2	D-1	D1	D2~D5	D6±1d	D28±2d	
Demographics	x						
Physical examination	x			x			
Vital signs ¹	x		x	x			x
Medical history:	Personal history	x					
	Past history	x					
	Allergy history	x					
	Tumor History	x					
Tumor stage	x						
Pathological examination ²	x						
Laboratory examination ³	Blood routine	x			x		x
	Blood Biochemistry	x			x		x
	Electrolyte	x			x		x
	Thyroid Function	x					
	Coagulation Function	x			x		x
	Urinalysis	x					
	Blood Pregnancy (If Needed)	x					
	Serum Virology	x					
12-lead ECG	x				x		x
Cardiac function score	x						
Physical condition score	x						
Chest X-ray (can be ignored if there is chest CT) ⁴	x						
CT/MRI/PET-CT ⁵	x						
Administration							
[⁶⁸ Ga]Ga-NOTA-SNA002 administration ⁶			x				
Biological Samples, Imaging, Safety Data, Specimen Collection							
Blood sampling ⁷			x				
Urine sampling ⁸			x				
Ada ⁹			x		x	x	x
Pet-ct ¹⁰			x				
Measurement of radiation dose ¹¹			x				
Formulate a Plan for Obtaining Target Lesion Specimens (If Performed) ¹²			x				
Collection of tissue samples from target lesions (if performed) ¹³				x			
Pd-111 immunohistochemical examination ¹⁴	x			x			
Other							
Examination of injection site ¹⁵			x	x			
Enrollment ¹⁶		x					
Out of group						x	
Concomitant medications ¹⁷	x	x	x	x	x		x

Study Period/Visits	Screening Period	Baseline Period	Study Period (5 days)		Safety Follow-up Period (D6-28)		Premature Withdrawal ¹⁸
Study Day (s)	D-14~2	D-1	D1	D2~D5	D6±1d	D28±2d	
Ac ¹⁸			x	x		x	x
Distribute/recycle journal cards						x	

1. Vital Signs: tested during the screening period, 6 ± 1 hours after D1 administration, and 6 ± 2 hours after D2 biopsy (if performed).
2. Pathological Examination: if the pathological examination results within one year before screening are obtained, and the subject receives biopsy samples within two weeks before enrollment and has not undergone chemotherapy, radiotherapy, or immunotherapy until enrollment, biopsy may not be performed after administration in this clinical trial.

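### The only scheduled pregnancy test can be 2 to 21 days old at the single D1 injection, and no newer pregnancy information is scheduled before dosing

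*Combined protocol and SAP*

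**What the plan says.** All references are to the combined protocol and SAP.

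- **Eligibility.** Exclusion 17 (section 5.2) bars pregnant or lactating women. It also bars "female subjects who have had unprotected sex within 2 weeks before screening, or with positive blood pregnancy test". Exclusions 17 and 18 deal with contraception.
- **Screening test.** Section 7.3.1, covering D-14 to D-2, lists a "serum pregnancy test (only for female subjects of childbearing age" among the laboratory tests of item 14. The same item gives serum virology a 28-day allowance, "while other laboratory tests can accept results within 7 days before screening".
- **Schedule.** The Table 4 row "Blood Pregnancy (If Needed" is marked in the screening column only.
- **D-1.** Section 7.3.2 has three items: "Review compliance with inclusion/exclusion criteria for the second time", enrolment, and concomitant medications.
- **D1 and later.** Section 7.3.3 contains no pregnancy test. Nor do the D6 laboratory tests or the early termination visit.
- **Dosing.** "SNA002 will only be intravenously injected once in the trial" (section 6.1.10). The activity "should be ranged from 37 to 200MBq" (section 6.1.5).
- **If pregnancy occurs.** Section 8.4.5 requires contraception advice before enrolment. For a pregnancy during the study it says "The pregnant subjects should immediately withdraw from the study", followed by recording, reporting and follow-up.

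**The concern.** The protocol clearly intends that no pregnant woman is injected, and it does not rely on contraception alone: exclusion 17 pairs a blood test with a two-week lookback. Both are tied to screening, while the exposure happens on D1. With one injection, a pregnancy found afterwards can be followed up but the exposure cannot be undone. Withdrawal could at most spare any remaining scans or a biopsy.

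A woman who conceives between the accepted test and D1, and does not know it, has nothing to report at the D-1 review. The investigator can complete every listed procedure and still inject her. At stake is direct exposure to a radionuclide and a first-in-human agent, given for imaging and with no therapeutic purpose. This is a subject-safety point. Dose escalation, sample size, endpoints and analyses do not depend on it.

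**Working it through.** **Stated figure first.** Section 6.1.9 gives about 42 days of participation, from up to 14 days of screening and up to 28 of follow-up: 14 + 28 = 42. This reproduces and fixes how early screening can start.

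**Age of the test at injection.** The schedule runs from D-1 to D1 with no day 0, so D-k is k days before D1. Age = k + days by which the result precedes screening.

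| Screening day | Result dated | Age at D1 |
|---|---|---|
| D-14 | 7 days earlier | 14 + 7 = 21 days |
| D-14 | same day | 14 days |
| D-2 | 7 days earlier | 2 + 7 = 9 days |
| D-2 | same day | 2 days |

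The range is 2 to 21 days (3 to 22 if a day 0 is counted). Note 3 of Table 4 repeats the 7-day allowance without naming the pregnancy test, but section 7.3.1 item 14 places the test and the allowance together. If the allowance did not apply, the maximum would be 14 days.

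**Gap in the lookback.** It ends at screening, so the uncovered interval is 2 to 14 days.

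**Maternal effective dose.** Section 6.1.7.1 gives 0.022 to 0.023 mSv/MBq, extrapolated from monkeys.

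- 37 × 0.022 = 0.81 mSv
- 185 × 0.022 = 4.07 mSv; 185 × 0.023 = 4.255 mSv (the protocol states about 4.1 mSv at 185 MBq)
- 200 × 0.023 = 4.60 mSv

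Low-dose CT adds to this, but its dose is not stated. The documents give no fetal dose.

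**Chance of at least one such dosing.** The rates needed are not in the documents. I assume that 10 to 30% of the 12 to 28 subjects are women of childbearing age (12 × 0.10 = 1.2 to 28 × 0.30 = 8.4 women), and that contraceptive failure f is 2 to 15% per year. With n women and a gap of t days, P = 1 − (1 − f)^(n·t/365.25).

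- All tests 21 days old: 0.14% (n = 1.2, f = 0.02) to 7.55% (n = 8.4, f = 0.15)
- Gap of 2 to 14 days only: 0.01% (n = 1.2, f = 0.02, t = 2) to 5.1% (n = 8.4, f = 0.15, t = 14)

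Each upper end sets every assumption at its maximum at once.

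**What a new test would gain.** A D-1 test would be 1 day old at injection and a D1 test 0 days. In calendar terms, 21 days to 1 is 1 − 1/21 = 95% shorter. That is not the reduction in risk, because a very early pregnancy tests negative. If detection lags conception by L = 7 to 14 days (assumed), a D1 test removes A/(A + L) of the undetectable conception time, where A is the age of the old test:

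- A = 21: 21/35 = 60% to 21/28 = 75%
- A = 14: 14/28 = 50% to 14/21 = 67%
- A = 2: 2/16 = 12% to 2/9 = 22%

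A test alone therefore helps least when screening is close to dosing. This is why the lookback needs extending too.

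**The case against.** The strongest reply is that several safeguards already exist. Contraception is required, subjects are counselled before enrolment, eligibility is reviewed again on D-1, and the investigator may order an unscheduled test. Some subjects will already be in hospital before D-1. The wording of the Table 4 row might be read as allowing a repeat test, and separate imaging procedures, not available here, may include a pre-injection check.

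Much of this stands, and it keeps the probability low. It does not close the gap. The Table 4 row is marked at screening only, section 7.3.1 ties the test's condition to childbearing age, and discretion to test is not a scheduled check. The D-1 review asks the right question but has no new scheduled result to answer it.

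Four stronger readings are tempting and are not supported:

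- **That section 8.4.5 is the safeguard and fails.** It governs reporting and follow-up once a pregnancy is known. The safeguards against exposure are exclusions 17 and 18 and the D-1 review, so the gap lies in sections 7.3.1 to 7.3.3, Table 4 and exclusion 17.
- **That a pregnant woman could be dosed without any deviation.** Exclusion 17 bars pregnancy itself, separately from a positive test, so dosing her would breach eligibility even if nobody knew. What can be said is that no scheduled check would detect it.
- **That the risk is near 7.6%, or that a new test removes 95% of it.** The first combines every upper assumption, and the second counts calendar days.
- **That no reproductive toxicity data exist.** The protocol describes monkey general toxicity, but the investigator's brochure is not among the documents, so this cannot be judged.

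**Conclusion.** The point holds as a weakness in the stated schedule. At the single injection the only scheduled pregnancy test can be 2 to 21 days old, and the unprotected-sex lookback leaves the last 2 to 14 days uncovered. These figures follow from the protocol's own windows, with no day 0 and with the 7-day allowance applied to the pregnancy test as section 7.3.1 reads.

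An unrecognised pregnancy could receive about 0.8 to 4.6 mSv maternal effective dose plus low-dose CT; fetal dose is unknown. The chance of this happening in the trial is low and cannot be fixed from the documents. The percentages in the working rest on assumed rates and only show the range. The case for change is that the exposure is irreversible and the check is cheap. It does not rest on frequency.

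**What to change.** 1. **Exclusion 17.** Extend the unprotected-sex lookback to run from 2 weeks before screening through D1, confirmed at the existing D-1 re-review and again before injection. Simply moving the two-week window to end at D1 would drop part or all of the period before screening that is covered now.
2. **Sections 7.3.2 or 7.3.3 and Table 4.** Add a pregnancy test for women of childbearing age, either on D-1 or as a rapid urine test on the pre-injection sample on D1, with a negative result required before injection. The Protocol Summary and Table 4 note 8 already plan a pre-injection urine sample, but item 6 of the D1 list in section 7.3.3 names only post-dose collections, so that list should be aligned.

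A serum sample drawn in the half hour before dosing should not be relied on, because the result may not be back in time. Section 8.4.5 needs no change.

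The lookback change needs no new procedure. The test costs one inexpensive assay per woman of childbearing age and adds no visit, although D-1 lists no sampling at present. An occasional false positive, or an exclusion under the longer lookback, may delay or cancel a dose. A very early pregnancy may still test negative, so some risk remains.

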8.5 Study Halting Rules

Administration of study agent will be halted when three grade 2 AEs determined to be “probably related” are reported to the IRC. The IRC will notify the study sponsor and investigators immediately when the third grade 2 event is reported, and enrollment screens will stop accepting new study participants.

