 - If the quality of the first 3 cases in the posterior dose group is higher than that in the prior, another 3 to 4 cases will be enrolled. After the completion of the posterior dose group, the IRC will discuss and decide whether this group should not be explored from the imaging aspect (e.g. The image quality of the first 3 cases in the 0.3mg dose group is higher than that in the 0.1mg dose group, then 3-4 cases continued to be enrolled in the 0.3mg dose group, and the subsequent dose exploration was not carried out, the 0.3mg dose was identified as the optimal image dose).
- 2) If the first three positive tumor lesions in a certain dose group judged by the IRC to present poor imaging quality (such as $T/B \leq 1$) or nonvisualization (functional imaging without nuclides), the decision of stopping enroll in this dose group can be made from an imaging perspective, and the dose group can directly increase to the next or second dose group (for example, if the imaging quality of the 0.1mg dose group is poor in three consecutive cases, the dose group can increase to the 0.3mg or 0.5mg dose group);
- 3) If the last dose group shows nonvisualization of the positive tumor lesions determined by the IRC in the first three cases, discussion will be conducted to determine whether to adjust the subsequent dose from the imaging perspective to explore or terminate the entire clinical trial.
- 4) After the dose escalation of all dose groups is completed, the imaging expert committee and the principal investigator will decide whether to continue enrolling 3-4 subjects in a certain initially identified optimal dose group for further exploration.

Security:

The principal investigator determines whether to increase the dose from the perspective of safety. Dose escalation should be stopped if one of the principles happen: ① If at least half of subjects in a dose group experience CTCAE grade 2 (or moderate) or above adverse reactions; ② or at least 1/3 subjects experience CTCAE grade 3 (or severe) or above adverse reactions; ③ or one serious adverse reaction in certain group.

The dose escalation will be determined by the principal investigator based on both imaging and safety results.

[figure not shown]
During the clinical trial, based on the principle of subject protection, the dose group can be rapidly escalated to the subsequent dose group if nonvisualization or the above safety events happens after only one subject is enrolled at the investigator's discretion.

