- 4) After the dose escalation of all dose groups is completed, the imaging expert committee and the principal investigator will decide whether to continue enrolling 3-4 subjects in a certain initially identified optimal dose group for further exploration.

Security:

The principal investigator determines whether to increase the dose from the perspective of safety. Dose escalation should be stopped if one of the principles happen:① at least half of subjects in a dose group experience CTCAE grade 2 (or moderate) or above adverse reactions;② or at least 1/3 subjects experience CTCAE grade 3 (or severe) or above adverse reactions;③ or one serious adverse reaction in certain group.

The dose escalation will be determined by the principal investigator based on both imaging and safety results. During the clinical trial, based on the principle of subject protection, the dose group can be rapidly escalated to the subsequent dose group if nonvisualization or the above safety events happens after only one subject enrolled according to the investigator's discretion.

[figure not shown]

Figure 3 Dose escalation

After the dose escalation of all dose groups is completed, the imaging expert committee and the principal investigator will decide whether to enroll another 3 or 4 patients in the identified optimal dose group.

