8.2.2 RELATIONSHIP TO STUDY AGENT

Correlation determination can be done using the five point method: relevant, highly likely related, possibly related, possibly unrelated, or unrelated. Dichotomy can also be used: relevant or unrelated (those that are relevant, highly likely related, or possibly related can be classified as "relevant" according to the dichotomy method; those that are unrelated or potentially unrelated can be classified as "unrelated" according to the dichotomy method).

Table 5 Classification and criteria for determining the correlation between adverse events in clinical drug trials

Five point method	Basis of determination	Dichotomy
Related	
 - Has a reasonable temporal relationship -Conforming to known drug mechanisms, characteristics, or known adverse reactions -De-excitation positive -No other plausible explanation -Re-excitation positive 	relevant
Probably	- Has a reasonable temporal relationship	

Related	
 -Conforming to known drug mechanisms, characteristics, or known adverse reactions -De-excitation positive -No other plausible explanation -Absence of Re-excitation positive proof. 	
Possibly Related	
 -Has a reasonable temporal relationship -Absence of re-excitation positive proof -Manifested as any of the following situations: 
 ①Conforming to known drug mechanisms, characteristics, or known adverse reactions, de-excitation positive, but other reasonable reasons can also be used for explanation. ② Conforming to known drug mechanisms, characteristics, or known adverse reactions, absence of de-excitation positive proof, and there are no other reasonable reasons to explain. ③Does not conform to the known mechanism of action, properties or known adverse reactions of the drug, de-excitation positive, and there is no other reasonable reason to explain. ④ Does not conform to the known mechanism of action, properties or known adverse reactions of the drug, de-excitation positive,also explained by other plausible reasons. ⑤ Does not conform to the known mechanism of action, , properties or known adverse reactions of the drug,absence of de-excitation positive proof, and no other plausible reason to explain. 	

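### Two safety rules misdirect if read literally: the single-subject sentence permits escalation after events that should stop it, and the 8.5 halt counts grade 2 without grade 3

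*Combined protocol and SAP*

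**What the plan says.** **Stopping escalation (6.1.7.2, Security).** Escalation should stop if any one of three things occurs:

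1. "at least half of subjects in a dose group experience CTCAE grade 2 (or moderate) or above adverse reactions"
2. "at least 1/3 subjects experience CTCAE grade 3 (or severe) or above adverse reactions"
3. "or one serious adverse reaction in certain group"

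**Single-subject sentence (same section, next paragraph).** Citing subject protection and leaving the matter to the investigator's discretion, it says the dose group can be "rapidly escalated to the subsequent dose group if nonvisualization or the above safety events happens after only one subject enrolled". The Protocol Summary carries the same rule: "nonvisualization or the above safety events happens after only one subject is enrolled".

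**Halting dosing (8.5).** "Administration of study agent will be halted when three grade 2 AEs determined to be" *probably related* and are reported to the imaging committee. The committee then notifies the sponsor and investigators "immediately when the third grade 2 event is reported", and enrolment closes.

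**Terminating the trial (5.4).** The trial ends if more than half of the subjects have a drug-related AE of grade 2 or greater, or on one drug-related SAE.

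**Causality (8.2.2, Table 5).** The scale has five levels, with *related* above *probably related*. A two-level version is also allowed: "Dichotomy can also be used: relevant or unrelated".

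**The concern.** Safety is a primary endpoint, and the protocol describes this as a first-in-human study. A site should be able to apply its stopping rules without guessing what was meant.

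The single-subject sentence makes sense for nonvisualization, where there is no reason to keep dosing at a mass that shows nothing. For toxicity it points the wrong way: it could be cited to give the next subject a higher dose straight after a reaction.

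Section 8.5 is the only numerical rule that stops dosing before an SAE without needing a proportion of subjects. The 6.1.7.2 criteria stop escalation, which does not by itself stop dosing in the current group. As worded, 8.5 counts the milder and less certain events and passes over the more severe and more certain ones.

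**Working it through.** The plan gives no operating figures for these rules, so there is none to reproduce. The only related figure is the sample size: 4 groups of 3 to 7 gives 4 × 3 = 12 to 4 × 7 = 28, as stated in 10.5.

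**Step 1. Stop criteria in a group of size n.** The smallest count meeting each fraction in 6.1.7.2 is:

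| n | grade 2+ (at least 1/2) | grade 3+ (at least 1/3) |
|---|---|---|
| 1 | 1 | 1 |
| 3 | 2 | 1 |
| 4 | 2 | 2 |
| 6 | 3 | 2 |
| 7 | 4 | 3 |

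At n = 1, one grade 2 reaction is 1/1, one grade 3 reaction is 1/1, and one serious reaction meets the third criterion directly. All three kinds of event that the single-subject sentence refers to should therefore stop escalation.

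**Step 2. Overlay 5.4.**
- A serious drug-related event in any group ends the trial.
- A grade 2 or greater related AE in the first subject dosed in the trial is 1/1, more than half, so the trial ends.
- In a later group, take three earlier subjects without reactions and one new subject with a non-serious grade 2 reaction. If 5.4 refers to the dose group, 1/1 ends the trial. If it refers to all dosed subjects, 1/4 = 25% does not.

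The sentence therefore has practical room only in that last case: a later group, a non-serious reaction, and the all-dosed reading of 5.4.

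**Step 3. Grade and causality across the rules.**

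| Rule | Grade counted | Causality | Action |
|---|---|---|---|
| 5.4 | 2 or greater | drug-related | end trial |
| 6.1.7.2 | 2 or above; 3 or above | adverse reaction | stop escalation |
| 8.5 | 2 | probably related | halt dosing |

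Read literally, three non-serious grade 3 events count 0 towards 8.5, and so do three grade 2 events rated *related*. Severe events that hospitalise or cause permanent or serious disability are SAEs under 8.1.2, as are life-threatening events and deaths. If drug-related, these end the trial under 5.4. The grade gap is the remainder, for example a severe reaction that restricts self-care without hospitalisation.

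**Step 4. A pattern that triggers nothing.** Suppose four groups of 7, each with 2 non-serious grade 3 reactions, judged when the group is complete. Then 2/7 = 28.6% is below 1/3 (3 of 7 needed), and 8/28 is not over half (15 needed). The 8.5 count is 0. If the fraction were checked after the first three subjects, 1 of 3 would stop escalation, so the example depends on when the check is made.

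**Step 5. Effect of rewording 8.5 on stopping.** Assumptions, none from the documents: at most one qualifying reaction per subject; rate r = 0.20; 20% of reactions are grade 3 or higher; half of those are serious; none is rated *related*. Per subject:
- grade 2: 0.20 × 0.80 = 0.16
- serious: 0.20 × 0.20 × 0.5 = s = 0.02
- non-serious grade 3: 0.02

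Stopping means three countable non-serious events (8.5) or one SAE (5.4). With q the per-subject chance of a countable non-serious event:

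P(stop) = 1 − Σ(k = 0 to 2) C(N,k) q^k (1 − q − s)^(N−k)

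- Current wording, q = 0.16: N = 12 gives 1 − (0.0924 + 0.2164 + 0.2322) = 0.46; N = 28 gives 1 − (0.0039 + 0.0211 + 0.0556) = 0.92.
- Reworded, q = 0.18: N = 12 gives 1 − (0.0687 + 0.1855 + 0.2296) = 0.52; N = 28 gives 1 − (0.0019 + 0.0122 + 0.0370) = 0.95.

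Range over the assumptions, from the same formula:

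| r | share of grade 3+ serious | s | q now → reworded | N = 12 | N = 28 |
|---|---|---|---|---|---|
| 0.20 | none | 0 | 0.16 → 0.20 | 0.30 → 0.44 | 0.85 → 0.94 |
| 0.20 | half | 0.02 | 0.16 → 0.18 | 0.46 → 0.52 | 0.92 → 0.95 |
| 0.20 | all | 0.04 | 0.16 → 0.16 | 0.58 → 0.58 | 0.96 → 0.96 |
| 0.10 | half | 0.01 | 0.08 → 0.09 | 0.17 → 0.19 | 0.54 → 0.60 |

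The fractions in 5.4 and 6.1.7.2 are left out of this calculation.

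**The case against.** The best defence is that other rules already cover most of the danger. One drug-related SAE ends the trial; grade 3 reactions in a third of subjects stop escalation; and the investigator and a safety committee (8.6) keep their judgement. The single-subject sentence permits rather than requires, and its appeal to subject protection suggests a drafting slip. Any sensible reader would take grade 2 in 8.5 to include grade 3.

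Most of this stands, and it limits the size of the problem. It does not remove the conflict: the same section says both stop and may go up, and 8.5 lacks an extension to higher grades that the protocol writes out elsewhere. A halting rule should not depend on what readers assume.

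Three stronger readings are tempting, and the documents do not support them:
- *That 8.5 could never fire if sites use the two-level causality scale.* Section 8.2.2 prints how the five levels map onto the two, and 8.5 names a five-level rating, so applying it presupposes that scale. Naming the scale in 8.5 settles the matter.
- *That 8.5 misses a large share of events because they are rated* related. Table 5 lists a positive rechallenge under that level, and 6.1.10 says the drug is given once, so the rating may be rare or unreachable in this trial.
- *That severe toxicity goes unchecked.* Drug-related SAEs are caught by 5.4.

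**Conclusion.** The point holds as two wording defects that should be corrected. Neither depends on assumed event rates.

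The single-subject sentence contradicts all three stop criteria. After allowing for 5.4, it can operate in later dose groups after a non-serious reaction, provided that over half in 5.4 means half of all dosed subjects. The 8.5 count omits higher grades and the rating *related*; after allowing for 5.4, the gap is mainly non-serious grade 3 reactions below the fractions in 5.4 and 6.1.7.2.

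The halt frequencies are illustrative and show only the price of the fix. That price depends strongly on the share of grade 3 or higher reactions that are serious, and is nil if all of them are. The unstated denominator in 5.4 is a secondary clarification.

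**What to change.** 1. In the single-subject sentence of 6.1.7.2 and its copy in the Protocol Summary, delete the reference to safety events, so that nonvisualization is the only ground for rapid escalation.
2. In 8.5, make the trigger: *three AEs of grade 2 or higher, assessed as probably related or related (five-point method, Table 5)*. Change the later reference to *the third such event*. State whether events or subjects are counted.
3. Secondary: in 5.4, say whether the half is of the dose group or of all dosed subjects. Only the first catches toxicity confined to one later group.

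The cost is a protocol amendment with ethics approval; no new data, patients or procedures are needed. The downside is somewhat more frequent halts, of the size shown in the check. If the sponsor finds that too frequent, it should raise the count of three, not leave out the more severe events.
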